### 3.1.1 Early Safety Review

There will be an initial safety phase of the study, in which 10 patients will be included (also randomized 4:1) to obtain some preliminary safety data and FSH values prior to the recruitment of the rest of the group under study.

These women will receive the study treatment over 3 weeks (8 will receive estriol vaginal gel and 2 placebo moisturizing gel). FSH levels in serum will be analysed at screening, baseline and at week 3 (day 22 +/- 3 days). An independent data monitoring committee (IDMC) will review the results (together with safety data) which will advise the chief investigators about a go /no-go decision with the other 60 patients to complete the study. The study will continue if no significant changes in FSH levels from postmenopausal to premenopausal levels are observed.

These 10 patients will be recruited in two sites in Spain, 5 patients in each one. These patients will have estrogens, and FSH and LH determined at screening, baseline and at week 3.

**Figura 2:** Study Design of the Initial Safety Phase

### 3.2 Duration of the study

It is estimated that the 60 patients will be recruited in approximately 3 months. These patients will receive study therapy for 12 weeks.

The first 10 patients for the early safety review will be recruited in approximately 1 month and treated for 3 weeks. The results of the FSH levels will be available in 2-3 additional weeks.

For safety reasons all patients will have a visit 30 (+/-5) days after finishing treatment with the study drugs/medications.

According to what is outlined above, the length of study will be approximately 11 months.

## 4. Study Population

Patients with hormone receptor positive and HER2 negative early breast cancer who are on treatment with NSAI and have vaginal atrophy.

### 4.1 Inclusion Criteria

Patients are eligible to be included in the study only if they **meet all** of the following criteria:

1. Written informed consent prior to beginning specific protocol procedures.
2. Patients must have histological confirmation of breast adenocarcinoma with stage I-III A, documented at a local pathology department.
3. The breast tumors must be estrogen-receptor positive and/or progesterone receptor positive ( $\geq 1\%$  of stained tumor cells by IHC as determined by the local laboratory) with any HER2 status.
4. Postmenopausal status defined as: 12 months of spontaneous amenorrhea or 6 months of spontaneous amenorrhea with serum FSH levels  $> 40$  mIU/ml or 6 weeks postsurgical bilateral oophorectomy with or without hysterectomy.
5. Patient must be receiving the non-steroidal aromatase inhibitors anastrozole or letrozole as breast cancer treatment in the adjuvant setting for a minimum of 6 months.
6. Women suffering from moderate to severe vaginal dryness according to the FDA guidelines for drug development in postmenopausal women (Center for Drug Evaluation and Research, CDER Jan 2003). A moderate symptom will be considered if the symptom is present, bothersome and annoying, and a severe symptom will be considered if the symptom is present, bothersome and annoying, and interferes with the normal patient activity.
7. Eastern Cooperative Oncology Group Performance Status (ECOG PS) of 0 or 1.
8. Adequate bone marrow as defined by the following laboratory values:
  - a. Absolute Neutrophil Count (ANC)  $\geq 1.5 \times 10^9/L$ .
  - b. Platelets (plt)  $\geq 100 \times 10^9/L$ .
  - c. Hemoglobin (Hgb)  $\geq 10$  g/dl.
9. Patient has adequate organ function as defined by the following laboratory values:
  - d. Serum creatinine  $\leq 1.5 \times$  ULN.
  - e. Bilirubin  $\leq 1.5 \times$  ULN.
  - f. Alkaline phosphatase  $\leq 2 \times$  ULN.
  - g. AST and ALT  $\leq 2 \times$  ULN.
10. Willingness and ability to comply with scheduled visits, treatment plan, laboratory tests and other study procedures.

## 4.2 Exclusion Criteria

Patients will be excluded from the study if they **meet any** of the following criteria:

1. Stage IIIB-IV breast cancer or bilateral breast cancer.
2. Treatment with any other current anti-tumoral therapy (chemotherapy, anti-Her2...etc) besides the NSAI. Pamidronate or Alendronate are permitted.
3. Prior history of other malignancy within 5 years of study entry, aside from non-melanoma skin cancer or carcinoma-in-situ of the uterine cervix adequately treated.
4. Postmenopausal uterine bleeding. Vaginal bleeding of unknown etiology.
5. Patients with endometrial thickness equal to or greater than 4 mm measured by transvaginal ultrasound.
6. Patients who have received any type of vulvovaginal treatment in the 15 days prior to the start of the study.
7. Use of any hormone, natural (phytoestrogens) or herbal products for the treatment of menopausal symptoms within the last 3 months.
8. Current or previous history of thromboembolic disease or coagulopathies.
9. Severe cardiovascular or respiratory diseases in the previous 6 months.
10. Renal Impairment.
11. Hepatitis B and/or hepatitis C carriers (unless with normal hepatic function).
12. Known human immunodeficiency virus infection.
13. Known hypersensitivity to NSAI.
14. Other severe acute or chronic medical or psychiatric condition, or laboratory abnormality that would impart, in the judgment of the investigator, excess risk associated with study participation or study drug administration, or which, in the judgment of the investigator, would make the patient inappropriate for entry into this study.
15. Previous investigational treatment for any condition or participation in any clinical trial within 4 weeks of inclusion date.

## 4.3 Discontinuations

### 4.3.1 *Discontinuation of Study Medication*

The criteria for enrollment must be followed explicitly. If a patient who does not meet enrollment criteria is inadvertently enrolled, that patient should be discontinued from the study medication, an exception may be granted if the patient, in the opinion of the investigator, is having benefit from the study medication. In these rare cases, the investigator must obtain documented approval from the sponsor to allow the patient to continue to receive the study drug.

Patients can be discontinued from the study therapy in the following circumstances:

- Patient's own request.
- Unacceptable toxicity.
- Tumor recurrence.
- Any clinical adverse event (AE), laboratory abnormality or inter-current illness which, in the opinion of the investigator, indicates that continued participation in the study is not in the best interest of the patient.
- Termination of the study by the sponsor.
- Physician's decision, including need of other anti-cancer therapy, not specified in the protocol.
- If the patient is non-compliant with study procedures.
- Loss of ability to freely provide consent through imprisonment or involuntarily incarceration for treatment of either a psychiatric or physical (e.g. infectious disease) illness.
- All patients will be discontinued from the treatment phase and they will perform the safety visit in case of a delay of more than 1 week during the daily administration phase or more than 2 weeks during the twice weekly administration phase, or permanent discontinuation of the study drug unless there is an obvious clinical benefit per the investigator's medical judgment and after discussion with the sponsor.

If possible, and after the permanent discontinuation of treatment, the patients will be assessed using the procedure normally planned for the last dosing day with the study treatment.

All permanent treatment discontinuation should be recorded by the Investigator in the eCRF when considered as confirmed.

#### ***4.3.2 Discontinuation of Study Sites***

Study Site participation may be discontinued if the sponsor, the investigator or the IRB of the study site judges it necessary for any reason.

#### ***4.3.3 Discontinuation of Study***

The study may be discontinued by the sponsor if this is medically reasonable and consistent with applicable regulations of Good Clinical Practice (GCP). Stopping the study for medical reasons may be required if patients experienced adverse reactions under the treatment with the study drug or if new information about the safety or effectiveness of the study drug justifies it.

### ***5.1.2 Vaginal gel placebo***

The placebo moisturizing gel has the same composition than Blissel® without the active drug substance, estriol.

The placebo moisturizing gel will be administered in the same way.

## **5.2 Materials and Supplies**

For this study, the term “study drug” (Investigational Medicinal Product [IMP]) refers to 0.005% estriol vaginal gel (Blissel®).

Placebo vaginal gel is the control medicinal product.

The Sponsor will provide to the study sites with Blissel® and Placebo for the purpose of this study.

Patients will be given three different packages:

- Baseline: tube of 30 g and 25 administration applicators. For weeks 1-3 of treatment.
- Week 3: tube of 30 g and 12 administration applicators. For weeks 4-8 of treatment.
- Week 8: tube of 30 g and 12 administration applicators. For weeks 9-12 of treatment.

### ***5.2.1 Storage, preparation and administration***

Storage conditions stated in the Study Reference Safety Document may be superseded by the label storage.

Investigators and site staff are reminded to continuously monitor room storage temperatures and ensure that thermometers are working correctly as required for proper storage of investigational product. Any temperature excursions must be reported immediately to the Sponsor and documented. Once a deviation is identified, the investigational product MUST be quarantined and not used until the Sponsor provides documentation of permission to use the investigational product.

Blissel® and placebo should be stored at controlled room temperature ( $\leq 25^{\circ}\text{C}$ ) in their original container.

Medication should be kept in a secured locked area at the study site in accordance with applicable regulatory requirements. Returned medication should be stored separately from medication that needs to be dispensed.

The investigator's team will hand over the medication to the patient. Patients will only be given the medication corresponding to each following period in the visits of day 1 (baseline visit) and in the visits of week 3 and week 8.

The Principal Investigator, Sub-Investigator, study nurse or the Gynecologist must explain to the patient how to administer the vaginal gel. It is advisable that the first application be performed in presence of the gynecologist or oncologist.

Women will be instructed to administer the gel themselves, preferably at bedtime, for the rest of applications.

### **5.2.2 Accountability**

The patient will be indicated to return both the tube and the unused applicators as surplus medication. The investigator will collect them and will record the number of unused applicators in each period in the eCRF in order to evaluate dosage compliance.

The surplus medication, the unused applicators in each period, will be stored until the end of the study. At that time they will be returned to the sponsor, which shall destroy them. All medication supplied for the study will only be used for this protocol and in no case for another purpose.

It is the responsibility of the investigator to ensure that a current record of Blissel® and placebo disposition is maintained at each study site where study drug is inventoried and disposed. Records or logs must comply with applicable regulations and guidelines.

GEICAM (on behalf of Sponsor) will provide forms to facilitate inventory control if the staff at the investigational site does not have an established system that meets these requirements.

## **5.3 Method of Assigning a Patient to a Treatment**

All patients will be screened prior to entry on this study. An explanation of the study and discussion of the expected side effects and presentation of the informed consent document will take place. Eligible and consenting patients will be enrolled into the study and a screening code will be assigned to the patients.

All patients who meet all inclusion and exclusion criteria will be randomized to receive 0.005% estriol vaginal gel (Blissel®) or placebo vaginal gel.

A randomization list will be generated taking into consideration blocks of 5 (4 actives 1 placebo). The study medication will be coded according to this randomization list. Study medications will be shipped in blocks of 5 to the sites.

In each site, all patients that fulfil all inclusion and exclusion criteria and are definitely included in the study will be assigned the randomization code. This code will be the one labelled in the medications. Thus, the first patient included in a site will receive the first study medication in the block, the second patient included will receive the second medication in the block, and this procedure will be followed consecutively.

The eligibility checklist must be completed and signed by the investigator prior to inclusion and it must be included into medical history of each patient.

All eligible patients enrolled in the study will be entered in a patient registration log maintained by the Site and in the Trial Master File.

The study treatment must be administered after definite inclusion of the patient in the study.

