### 3. Investigational Plan

#### 3.1 Study Design

This is a phase II, prospective, randomized, double-blind, placebo-controlled, international (Spain and Sweden) and multicentre study.

Sixty patients will be randomized (stratified by site) to receive 0.005% estriol vaginal gel (arm A) and placebo moisturizing gel (arm B) in a 4:1 proportion, so 48 patients will enter in arm A and 12 in arm B. Patients will undergo gynaecological tests, plasma and serum extraction for hormone determinations, adverse events collection and will answer a questionnaire according to what is outlined in Figure 1.

A) Patients randomized to Arm A (experimental arm) will receive:

Investigational drug product: 0.005% estriol vaginal gel (Blissel®)

Route: Vaginal. Administration by an applicator inserted deep inside the vagina

Dose: 1 g of gel, containing 50 µg of estriol

Dosage schedule: Weeks 1-3: single daily application  
Weeks 4-12: twice weekly administration.

[figure not shown]
Women will be instructed to administer the gel at bedtime.

B) Patients randomized to Arm B (control arm) will receive:

Placebo moisturizing gel (vehicle of Blissel®).

Same route and dose schedule than Blissel®.

**Figure1.** Study Design

[figure not shown]

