### **5.8.1 Process for urgent unblinding**

In general, unblinding of participants during the conduct of the clinical trial is not allowed unless there are compelling medical or safety reasons to do so.

Any serious adverse event considered by the investigator to be related to the blinded treatment medication (0.005% estriol vaginal gel/placebo vaginal gel) should be reported as such to the sponsor via the appropriate SAE reporting form.

There will be two complete sets of randomization codes. One will be kept by the GEICAM Pharmacovigilance department and the other will be distributed among the investigators. The emergency codes should be kept in a safe but accessible place in the event they should be opened. Each investigator will receive the necessary envelopes closed to randomize a determined number of patients. Each envelope will contain the details of the treatment that the patient is receiving. In the case of emergency the envelope must be opened to determine the treatment being administered.

The randomization envelopes can only be opened in an emergency. When the investigator opens the envelope he/she must record the date, the time and the reason he/she has had to do so and will keep this information with the eCRF documentation. He/she should also immediately inform the study monitor that a treatment code has been opened. As per regulatory reporting requirement, it will unblind the identity of the study medication for all unexpected SAES that are considered by the investigator to be related to the study drug. Details of subjects who are unblinded during the study will be included in the Clinical Study Report.

---

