The differentiation between active and placebo in the subjective parameters of efficacy (secondary) would be possible at the expense of a sample size noticeably superior. Since the evaluation of effectiveness is not primary but secondary in this study, it is not justified in this study to increase the sample for this reason.

In accordance with the above, the study would include 55 women. 44 will receive vaginal estriol gel and 11 with the placebo moisturizing gel). Taking into account 10% of dropouts, the sample to be considered is of 60 women (48 vaginal estriol gel and 12 placebo moisturizing gel). This is an unbalanced study but with an active: placebo ratio of 4:1, which will support an adequate patient randomization (blocks of 5).

10 additional women will be recruited in a first safety phase of the study (8 with vaginal estriol gel and 2 placebo moisturizing gel).

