#### **9.4.2 Protocol Signatures**

After reading the protocol, each principal investigator will sign the protocol signature page and send a copy of the signed page to Sponsor.

---

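### The protocol tells investigators that site blocks are always five with exactly one placebo, so an emergency code-break on a placebo woman also unblinds the rest of her block

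*Protocol*

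**What the plan says.** Section 5.3 fixes the allocation scheme: "A randomization list will be generated taking into consideration blocks of 5 (4 actives 1 placebo"). It adds that "Study medications will be shipped in blocks of 5 to the sites" and that "the first patient included in a site will receive the first study medication in the block", with later patients following consecutively. Section 3.1 makes the lists site-specific: "Sixty patients will be randomized (stratified by site"). Section 8.1 repeats the block length, saying of the 4:1 ratio that it is one "which will support an adequate patient randomization (blocks of 5"), and the sample-size paragraph of the synopsis does the same. No second or random block size appears anywhere, and nothing confines the scheme to a restricted document.

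The text reaches the sites. Under section 9.4.2, after reading the protocol, "each principal investigator will sign the protocol signature page".

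On code-breaking, section 5.8.1 provides two sets of codes: "One will be kept by the GEICAM Pharmacovigilance department and the other will be distributed among the investigators". Each envelope shows one patient's treatment. Section 5.8 lets the site principal investigator, or an authorised person, unblind when care requires it. The same section says that staff directly involved are to remain unaware of treatment until the database is closed.

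**The concern.** An emergency code-break should reveal one woman's treatment. Under a published block of five with a single placebo it can reveal five. Kits are used in order, so site staff can work out block membership from the order of inclusion alone. Once a placebo woman is known, the allocation of every other woman in her block follows, including the treatment that the next candidate would receive.

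The site team scores three mucosal signs from 0 to 3 (section 8.2.7.1), reads the pH strip by colour (6.4) and judges adverse-event causality (6.3.3). The investigator also decides on discontinuation (4.3.1) and can exclude a candidate on judgement (4.2, criterion 14). Each of these could be done with knowledge of treatment. With only 12 placebo women planned, one affected block touches 1 of 12 placebo women and 5 of 60 overall.

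**Working it through.** **Inputs.** Block of 5 with 4 active and 1 placebo (5.3); 60 women, 48 and 12 (3.1); about 5 sites (synopsis); recruitment in about 3 months (3.2).

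**The plan's own figure.** 60 / 5 = 12 blocks; 12 × 4 = 48 estriol and 12 × 1 = 12 placebo. This reproduces the stated split, provided that every site fills its blocks.

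**What one known allocation reveals.** For a block of size B with P placebos, once one placebo is known, the chance that any other given member is on estriol is (B − P)/(B − 1).

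| Block | Known woman | Chance that another member is on estriol | Any other allocation certain? |
|---|---|---|---|
| 5 (4:1) | placebo | 4/4 = 1 | yes, all four |
| 5 (4:1) | estriol | 3/4 = 0.75 | no |
| 10 (8:2) | placebo | 8/9 = 0.889 | no |

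With nothing known, the chance of placebo is 1/5 = 20%. One known estriol woman raises it to 1/4 = 25% for each other member.

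**Average yield of one code-break.** If the woman is in effect random with respect to treatment, she is on placebo with probability 0.20. The number of others revealed with certainty is on average 0.20 × 4 = 0.8. This is an upper figure: if the site's last block is incomplete, fewer than four others exist to be revealed.

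**Scale in the trial.** The protocol gives no expected number of code-breaks. Assuming 0 to 2, the expected number of other women revealed is 0 to 2 × 0.8 = 1.6, out of 60.

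**Time window for steering enrolment.** 60 / 5 sites = 12 women per site in about 3 months, or 4 per month. A block of 5 then fills in about 5/4 = 1.25 months, roughly five weeks. Only a code-break in that window can affect women of the same block who are not yet enrolled.

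**Does a non-responder give the same certainty?** Take the maturation-value assumptions in section 8.1 (mean change 24.9 on estriol, 0.6 on placebo, SD 24.2) and assume normality. For a woman with zero change, the likelihood ratio for placebo is exp[(24.9² − 0.6²)/(2 × 24.2²)] = exp(619.65/1171.28) = 1.70. Her chance of placebo becomes 0.20 × 1.70/(0.20 × 1.70 + 0.80) = 0.34/1.14 = about 30%. She is still about 70% likely to be on estriol.

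**Mixed blocks of 5 and 10.** Assume that both sizes are equally likely and that staff cannot tell which applies. A known placebo woman is in a block of 10 with probability 2/3, because that block holds two placebos against one. The chance that another member of her block is on estriol is 1/3 × 1 + 2/3 × 8/9 = 0.926. No other allocation is then certain to the site.

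**The case against.** The strongest reply is that very few events can trigger the leak. Section 5.8.1 allows a code-break only for compelling medical or safety reasons, requires the date, time and reason to be recorded, and requires the monitor to be told. Four in five random code-breaks would show estriol and reveal little. The 4:1 ratio already tells every investigator that a woman is 80% likely to be on estriol, so even certainty adds only 20 percentage points. All of this stands and limits the size of the point.

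Stronger readings are tempting, and the protocol does not support them:

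- **Expedited safety reports as a leak.** A reader might infer that they reveal the arm to sites. Section 6.3.5 says that investigators receive these notices without treatment-arm information.
- **Obvious non-response as a leak.** It yields a guess, as the likelihood ratio of 1.70 shows. The comparator is the moisturising vehicle, matched in appearance, aroma and texture (5.8). Section 8.1 itself says that separating the arms on subjective efficacy would need a noticeably larger sample.
- **Bias in the main result.** FSH and LH, the estrogens and the maturation value are all determined in central laboratories (6.1, 6.2, 6.4), and the FSFI is completed by the patient (6.5). Assessor knowledge does not enter those readings.

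What survives is the envelope route. It is written into the protocol, and when it meets a placebo woman the inference about her block is exact.

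**Conclusion.** The point holds as a minor weakness in blinding and allocation concealment. The protocol discloses one fixed block size with exactly one placebo, so a code-break on a placebo woman makes every other allocation in her block certain. That works against the rule in section 5.8 that staff stay unaware until the database is closed. The expected size is small: at most 0.8 other women per random code-break, and 0 to 1.6 of 60 under the assumed 0 to 2 code-breaks.

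The outcomes exposed are investigator-scored signs, pH strip reading, causality judgements, discontinuation decisions and selection of the next woman. A reader might infer that all 12 blocks are compromised or that the FSH comparison is in doubt. The first is only a theoretical vulnerability that needs a placebo woman to be identified in each block. The second does not follow, because FSH could be touched only indirectly, through discontinuation or selection.

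The conclusion assumes that the same blocks are used as printed and that no separate document already varies them. Such a document would help, but the printed scheme would remain in the investigators' hands until the protocol text is changed.

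**What to change.** Before the 60 women are recruited:

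1. Generate the site lists with randomly mixed blocks of 5 and 10. Both sizes keep the 4:1 ratio.
2. Hold block sizes and composition in a restricted randomisation document that site staff do not see.
3. Remove block size and composition from the synopsis and sections 5.3 and 8.1, including the sentence on shipment in fives. The 4:1 ratio can stay.
4. Number and ship kits without visible block boundaries.

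The cost is a new list, a wording change, slight kit overage and a marginally looser 48:12 split. The split is not guaranteed now either: about 12 women per site is two full blocks and part of a third. The arrangements for emergency unblinding need not change for this point.
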